4.1.1. Additional Inclusion Criteria for Subjects without Hepatic Impairment (Cohort 1, only)

1. Male and/or female subjects –
 - a. No clinically relevant abnormalities identified by a detailed medical history, full physical examination, including blood pressure and pulse rate measurement, 12-lead ECG and clinical laboratory tests, as assessed by the sponsor-identified central laboratory;
 - b. Breath alcohol test at Screen must be negative;
2. Subjects must fit the demographic-matching criteria, including –
 - a. A body weight that is ± 10 kg of the average of the pooled hepatic impairment cohorts (Cohorts 2, 3, and 4), as provided by the sponsor;
 - b. An age that is ± 5 years of the average of the pooled hepatic impairment cohorts (Cohorts 2, 3, and 4), as provided by the sponsor;

- c. ***Attempts will be made*** to ensure that the male-to-female distribution in Cohort 1, is comparable, to that in the pooled hepatic impairment cohorts (Cohorts 2, 3, and 4);
3. No known or suspected hepatic impairment; including at Screening, meet **all** the following criteria, as assessed by the sponsor-identified central laboratory, with a single repeat permitted to assess eligibility, if needed:
 - ALT \leq upper limit of normal (ULN);
 - AST \leq ULN;
 - Total bilirubin \leq ULN;
 - **NOTE:** Subjects with a history of Gilbert syndrome (and hence elevated total bilirubin) are eligible provided direct bilirubin level is \leq ULN **plus** ALT and AST are \leq ULN **plus** alkaline phosphatase, hemoglobin, **and** reticulocyte count are all \leq ULN;
 - Albumin \leq ULN;
 - Prothromin time \leq ULN.

4.1.2. Additional Inclusion Criteria for Subjects with Impaired Hepatic Function (Cohorts 2, 3, and 4, only)

1. Satisfy the criteria for Class A, B, **or** C of the modified Child-Pugh classification (refer to [Appendix 2](#));
2. A diagnosis of hepatic dysfunction due to hepatocellular disease (and not secondary to any acute ongoing hepatocellular process) documented by medical history, physical examination, liver biopsy, hepatic ultrasound, computerized tomography scan, **or** magnetic resonance imaging (MRI);
3. Stable hepatic impairment, defined as no clinically significant change in disease status within the 28 days prior to the Screening Visit, as documented by the subject's recent medical history (**for example:** no worsening clinical signs of hepatic impairment, no worsening of total bilirubin or prothrombin time [PT] by more than 50%);
4. Stable concomitant medications (as defined in [Section 5.8.2](#)) for the management of individual subjects medical history; **on a case-by-case basis**, with input from the Sponsor, subjects receiving fluctuating concomitant medication/treatment may be considered if the underlying disease is under control;
5. **Previous** history of alcohol abuse is permissible provided that the subject is willing and able to abide by the lifestyle guidelines described in [Section 4.4.2](#) of this protocol **and** breath alcohol test, at Screen, is negative.

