1.3.1. Rationale for Study Population

The reference set of subjects (Cohort 1, demographic-matched subjects without hepatic impairment) will be characterized as subjects with no chronic medical conditions, and no significant abnormalities in clinical laboratory tests and other procedures conducted at Screening.

The Child-Pugh classification system (refer to [Appendix 2](#)) will be used to define the three cohorts of subjects with varying degrees of hepatic impairment (Cohorts 2 to 4, inclusive), in this study; with the reference being subjects without hepatic impairment. All three categories of hepatic impairment will be assessed as this represents the likely population in later phase studies for the proposed indication (treatment of NASH with fibrosis). In addition to alanine aminotransferase (ALT), total bilirubin and aspartate aminotransferase (AST) will be assessed in this study as per the recommendations of the National Cancer Institute Organ Dysfunction Working Group Criteria for assessment of hepatic impairment.⁹ Notably, the historical requirement of an encephalogram for encephalopathy grading will not be required. This study will include subjects with mild (Child-Pugh Class A, Cohort 2), moderate

090177e190d319bb\Approved\Approved On: 29-Apr-2019 07:31 (GMT)

(Child-Pugh Class B, Cohort 3), and severe (Child-Pugh Class C, Cohort 4) hepatic impairment as well as demographic-matched control subjects, without hepatic impairment. All subjects will be required to offer their own consent to participate in this study; as such subjects with clinically active Grade 3 or Grade 4 encephalopathy (refer to [Appendix 2](#)) will be excluded. However, subjects who have a *previous* history of Grade 3 or 4 encephalopathy but are *currently* receiving an intervention [for example: lactulose or lactitol, alone or in combination with rifaximin, and/or neomycin] to control their encephalopathy-related signs and symptoms are eligible provided the *on-treatment* encephalopathy grading at the Screening visit is Grade 2 or lower thereby permitting them to provide informed consent. Acknowledging the medical state of the population enrolled, certain eligibility criteria for subjects with hepatic impairment are purposefully, distinctly different, including assessment of Hepatitis B and Hepatitis C, with no specific exclusion of those who have these conditions planned for subjects classified in Cohorts 2, 3, or 4 (refer to [Section 4.1.2](#) and [Section 4.2.2](#)).

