3. STUDY DESIGN

3.1. Study Overview

This is a non-randomized, open-label, single-dose, parallel-cohort, multisite study to investigate the effect of varying degrees of hepatic impairment on the plasma pharmacokinetics (total and unbound) of PF-05221304 after a single oral 25 mg dose administered in the fed state. A total of approximately 24 subjects with varying degrees of hepatic function will be enrolled into the study to ensure that up to 6 evaluable subjects in each of the 4 hepatic function cohorts complete the study. Subjects will be selected based on their Child-Pugh score as shown in Table 1.

Table 1. Hepatic Function Categories Based on Child Pugh Score

Cohort	Description	Child-Pugh Score	Number of Subjects
1	Without hepatic impairment	Not Applicable	6 ^a
2	Mild hepatic impairment	Class A (5 to 6 points)	6
3	Moderate hepatic impairment	Class B (7 to 9 points)	6
4	Severe hepatic impairment	Class C (10 to 15 points)	6 ^b

[figure not shown]
a. Additional subjects *may* be dosed to a maximum of 10 subjects to ensure mean age is ± 5 years and mean body weight ± 10 kg of this cohort is in line with pooled average assessed when $\geq 75\%$ of subjects are dosed across other 3 cohorts.

b. If recruitment across the sites selected proves to be prohibitive, study will dose only 4 subjects in this cohort.

Child-Pugh scores will be determined as described in [Appendix 2](#), at the screening visit. Recruitment for subjects meeting the criteria for Cohorts 3 and 4 will initiate first. Recruitment for subjects in Cohort 2 will start when approximately 50% of total subjects across Cohorts 3 and 4 (ie, 6 of 12) have been dosed. Subjects in Cohort 1 will be recruited last to match the average demographics (at a minimum, age and weight; and as much as practically possible gender) across the pooled Cohorts 2 through 4. Approval from the Sponsor must be garnered *before* proceeding with dosing subjects in Cohort 1.

The overall study design is summarized below in [Figure 1](#). For individual subjects, the total duration of participation from the Screening Visit to the on-site Follow-up Visit (Day 7) will be a minimum of approximately 3 weeks and a maximum of approximately 5 weeks.

Figure 1. C1171006 Study Design

In this study, subjects who prematurely discontinue for non-safety related reasons may be replaced, at the discretion of the principal investigator (PI) and Sponsor study team.

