7. Other acute or chronic medical or psychiatric condition including recent (within the past year) or active suicidal ideation or behavior or laboratory abnormality that may increase the risk associated with study participation or investigational product administration or may interfere with the interpretation of study results and, in the judgment of the investigator, would make the subject inappropriate for entry into this study.

4.2.2. ***Additional*** Exclusion Criteria for Subjects with Impaired Hepatic Function (Cohorts 2, 3, and 4, ***only***)

In addition, subjects in the hepatic impairment cohorts (Cohorts 2, 3 and 4) presenting with ***any*** of the following will ***not*** be included in the study:

1. Hepatic carcinoma ***or*** hepatorenal syndrome ***or*** limited *predicted* life expectancy (defined as less than 1 year in Cohorts 2 & 3 and less than 6-months for Cohort 4 ***only***);
2. History of surgery that would be expected to alter Absorption, Distribution, Metabolism and Excretion (ADME) properties of PF-05221304 – ***for example***: status post porta-caval shunt surgery;
 - ***NOTE***: Subjects with a transjugular intrahepatic portosystemic shunt (TIPS) are permitted provided that they meet the Child-Pugh criteria;
3. History of gastrointestinal hemorrhage due to esophageal varices or peptic ulcers less than **4 weeks** prior to Screening;
4. At Screening, subjects with an estimated glomerular filtration rate (eGFR) of ≤ 60 mL/min using the Modification of Diet in Renal Disease (MDRD) equation, and serum creatinine (SCr), as assessed by the sponsor-identified central laboratory, with a single repeat permitted to assess eligibility, if needed;
5. Signs of clinically active Grade 3 or 4 hepatic encephalopathy (ie, $>$ Grade 2 Portal Systemic Encephalopathy score) – refer to [Appendix 2](#);
6. Severe ascites and/or pleural effusion, ***except*** for those categorized in Cohort 4 who may be enrolled provided subject is medically stable, per Investigators' medical judgment;
7. Subjects who have previously had a transplanted kidney, liver, or heart;
8. Screening ***supine*** 12-lead ECG demonstrating a QTcF interval >470 msec ***or*** a QRS interval >120 msec. If QTcF exceeds 470 msec, ***or*** QRS exceeds 120 msec, the ECG should be repeated 2 more times and the average of the 3 QTcF or QRS values should be used to determine the subject's eligibility;

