Appendix 2. Child-Pugh Classification (CPC) of Liver Dysfunction

Table 2-1: Scoring for Child-Pugh Classification

Cohort	CPC	Level of dysfunction	Total Score (tally based on assessment of parameters in Table 2-2)
1	Not Applicable	Without hepatic impairment	Not Applicable
2	A	Mild	5-6
3	B	Moderate	7-9
4	C	Severe	≥10

Table 2-2: Derivation of Child-Pugh Classification Score

Assessment Parameters	Assigned score for observed findings		
	1 point	2 point	3 point
Encephalopathy grade ^a (refer to Table 2-3 below)	0	1 or 2	3 or 4 ^a
Ascites	Absent	Asymptomatic	Requiring intervention
Serum total bilirubin, mg/dL	<2	2 to 3	>3
Serum albumin, g/dL	>3.5	2.8 to 3.5	<2.8
Prothrombin time, sec prolonged	<4	4 to 6	>6

- a. Subjects with a prior history of Grade 3 or 4 encephalopathy who are *currently* receiving an intervention [for example: lactulose or lactitol, alone or in combination with rifaximin, and/or neomycin] to manage encephalopathy-related signs and symptoms should be scored for encephalopathy grading *based on their presentation while on intervention at the Screening visit* and can be included in Study C1171006 so long as they do **not** have clinically active Grade 3 or 4 encephalopathy.

Table 2-3: Determination of Encephalopathy Grade

Encephalopathy Grade	Definition
0	Normal consciousness, personality, neurological exam
1	Restless, sleep disturbed, irritable/agitated, tremor, impaired handwriting
2	Lethargic, time-disoriented, inappropriate, asterixis, ataxia
3 ^a	Somnolent, stuporous, place-disoriented, hyperactive reflexes, rigidity
4 ^a	Unrousable coma, no personality/behavior, decerebrate

- a. Subjects with clinically active Grade 3 or 4 encephalopathy are excluded.

CPC should be assessed at Screening, only to determine the classification of a given subject.

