8.2. Statistical Analyses of PK Parameters

One-way analysis of variance (ANOVA) will be used to compare the natural log transformed PF-05221304 AUC_{inf} , AUC_{last} and C_{max} , unbound AUC_{inf} ($AUC_{inf,u}$), unbound AUC_{last} ($AUC_{last,u}$), and unbound C_{max} ($C_{max,u}$), as data permit, for each of the hepatic impairment classification cohorts (Test) to the cohort without hepatic impairment (Reference). Estimates of the adjusted mean and corresponding 90% confidence intervals will be obtained from the model for each cohort. Estimates of the adjusted mean differences (Test-Reference) and corresponding 90% confidence intervals will be obtained from the model as well. The adjusted mean estimates and adjusted mean differences and 90% confidence intervals for the estimates and differences will be exponentiated to provide estimates of adjusted geometric means and estimates of the ratio of adjusted geometric means (Test/Reference) and 90% confidence intervals for the estimates and for the ratios respectively (see Appendix 1 for SAS code).

Additionally, as an exploratory analysis, age, body weight, and gender (see Section 6.4) will be explored as a covariate/factor in the ANOVA/ANCOVA model, as appropriate (see Appendix 1 for SAS code).

Linear regression may be used to analyze the potential relationship between the following PK parameters -AUC_{inf}, and CL/F separately - and the following hepatic function - serum albumin, prothrombin time, and total bilirubin separately -. Estimates of the slope and intercept, together with their precision (90% confidence interval [CI]), and the coefficient of determination (ie R-squared and adj-R-squared) will be obtained from the model.

Plots of PK parameters -AUC_{inf}, and CL/F separately - versus hepatic function - serum albumin, prothrombin time, total bilirubin separately - will be constructed. A regression line and 90% confidence region for the PK parameters and hepatic function will be included. (See appendix 1 for example of SAS code to produce the figure).

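### The Cohort 1 albumin criterion has an upper limit and no lower one, so it cannot screen out the low albumin that Appendix 2 scores as hepatic impairment

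*Protocol*

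**What the plan says.** Protocol 1.3.1 describes Cohort 1 as having "no significant abnormalities in clinical laboratory tests and other procedures conducted at Screening". Section 4.1.1 turns that into eligibility rules. Criterion 3 begins "No known or suspected hepatic impairment; including at Screening, meet" and requires every item in a list of central-laboratory limits, with one repeat allowed. ALT, AST, total bilirubin, albumin and prothrombin time are each held at or below the ULN, apart from an allowance for Gilbert syndrome on bilirubin. No lower limit for albumin appears in this list or elsewhere in the Cohort 1 criteria.

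Appendix 2 Table 2-2 sets the Child-Pugh scoring for the row "Serum albumin, g/dL": above 3.5 scores 1 point, 2.8 to 3.5 scores 2, and below 2.8 scores 3. The SAP repeats the same bands in its section 2.1. Table 1 in Protocol 3.1 marks the Child-Pugh score as not applicable to Cohort 1.

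**The concern.** The criterion exists to show that controls have no hepatic impairment. For ALT, AST, bilirubin and prothrombin time, an upper limit does that work. For albumin, the protocol's own scoring treats a fall as the sign of impairment, so an upper limit points the wrong way. A subject with low albumin passes the only explicit albumin rule. A subject just above the ULN fails it.

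This matters because Cohort 1 is the Reference for every planned Test/Reference ratio, total and unbound (Protocol 9.3.3, SAP 8.2). It is also small: 6 subjects are planned, with a maximum of 10. In the one-way ANOVA on the log scale each control therefore carries between 1/10 and 1/6 of the Reference mean. The rule is operative, because Protocol 4.3 makes dosing on Day 1 conditional on the eligibility criteria.

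**Working it through.** The plan states no figure to reproduce. The check is of direction: which Table 2-2 bands the bullet accepts and which it rejects.

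**Inputs**
- Rule: accept if albumin is at or below the ULN (Protocol 4.1.1, criterion 3).
- Bands: above 3.5 g/dL = 1 point; 2.8 to 3.5 = 2 points; below 2.8 = 3 points (Appendix 2, Table 2-2).
- ULN: not given in the documents. Assumed, and varied from 3.5 to 5.5 g/dL.

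**Method.** Take albumin from 1.0 to 7.0 g/dL in steps of 0.1, which gives 61 values: 18 in the 3-point band, 8 in the 2-point band and 35 in the 1-point band (18 + 8 + 35 = 61). Apply the rule and count rejections by band. These are counts of grid values, not of people.

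| Assumed ULN (g/dL) | Rejected, 3-point band | Rejected, 2-point band | Rejected, 1-point band |
|---|---|---|---|
| 3.5 | 0 of 18 | 0 of 8 | 35 of 35 |
| 4.5 | 0 of 18 | 0 of 8 | 25 of 35 |
| 4.8 | 0 of 18 | 0 of 8 | 22 of 35 |
| 5.0 | 0 of 18 | 0 of 8 | 20 of 35 |
| 5.2 | 0 of 18 | 0 of 8 | 18 of 35 |
| 5.5 | 0 of 18 | 0 of 8 | 15 of 35 |

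At every assumed ULN, neither band scored above 1 point loses a value, and every rejection falls in the least-impaired band. The result needs only a ULN of 3.5 g/dL or more.

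**The limit reversed.** With a lower limit at an assumed 3.5 g/dL (accept if albumin is at or above 3.5), the rule rejects 18 of 18 values in the 3-point band, 7 of 8 in the 2-point band and 0 of 35 in the 1-point band. The one 2-point value that still passes is 3.5 itself, because Table 2-2 requires more than 3.5 for 1 point.

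**Illustration only.** With the other four Child-Pugh items at 1 point each, the subtotal is 4. Albumin above 3.5 then gives 4 + 1 = 5, albumin of 2.8 to 3.5 gives 4 + 2 = 6, and albumin below 2.8 gives 4 + 3 = 7, the lowest Class B score in Table 1. The protocol does not apply the score to Cohort 1, and a person with all five items at their best still scores 5, which is Class A. The tally shows the direction of the scoring and is not a measure of harm.

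**The case against.** The strongest reply is that the bullet does not stand alone. A control with low albumin must also satisfy the lead clause of criterion 3 and inclusion 1a, "No clinically relevant abnormalities identified by a detailed medical history, full physical examination", which expressly extends to central-laboratory tests. Albumin is in that panel (Table 2), so the investigator will see the value. Cohort 1 exclusions in 4.2.1 add more: evidence of chronic liver disease, including hepatitis B and C testing (exclusion 1); clinically significant disease, including hepatic, renal and gastrointestinal (exclusion 3); and a laboratory abnormality that "may interfere with the interpretation of study results" (exclusion 7).

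Most of this stands, and it limits the consequence. Two things remain. None of these clauses sets an albumin limit, and they rest largely on judgment. Nor can any of them undo the opposite error: because every listed limit must be met, a control whose albumin stays above the ULN on the permitted repeat has to be rejected.

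A reader might infer three stronger things that the documents do not support:
- **That impaired subjects will be enrolled as controls, or that the exposure ratios are biased.** Passing one bullet does not make a subject eligible, and nothing in the documents allows a bias to be calculated.
- **That the planned regressions on serum albumin are compromised.** The SAP makes them optional, and each subject would enter at the measured value.
- **That the ULN limit on hemoglobin in the Gilbert note is the same error.** That depends on a purpose for the limit which the protocol does not state.

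**Conclusion.** The concern holds as a wrongly directed eligibility limit in the definition of the Reference cohort. The only explicit albumin rule rejects 0 of the 2 bands that Table 2-2 scores as impaired and can turn away only controls in the least-impaired band. This rests on one assumption, a ULN of at least 3.5 g/dL. The available text gives no reason for an upper limit.

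The expected effect on the Reference cohort is small, since the judgment-based clauses and the correctly directed limits on the other tests would probably exclude most low-albumin subjects. The size of any effect on the PK comparisons is not quantified. No sample-size or precision figure depends on this rule. It should be corrected because it is wrong as written and cheap to put right.

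**What to change.** Reconcile the albumin bullet in Protocol 4.1.1 criterion 3 with Appendix 2 by replacing the upper limit with a lower one. The sponsor should choose the threshold and state it. Either basis is defensible: the 1-point band of Table 2-2 (above 3.5 g/dL) or the central laboratory's lower limit of normal. The two need not agree. The documents give no lower limit of normal, and one at or below 3.5 g/dL would still admit some 2-point values, so the protocol should say which basis is meant.

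The cost is one line of one criterion. Albumin is already in the laboratory panel run at Screening (Table 2), so no test or blood volume is added. The downside is possibly a few more screen failures among controls.

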4.2. Exclusion Criteria

Subjects in all 4 Cohorts with **any** of the following characteristics/conditions will **not** be included in the study:

1. Any condition possibly affecting drug absorption (eg, prior bariatric surgery, gastrectomy, ileal resection) –
 - **NOTE**: subjects who have undergone cholecystectomy and/or appendectomy are eligible for this study so long as the surgery occurred more than 6 months prior to Screening;
2. A positive urine drug test, for illicit drugs, at Screening;
 - **NOTE**: repeat urine drug testing is **not** permitted in this study;
3. Participation in other studies involving investigational drug(s) within **30 days** (or as determined by the local requirement) or 5 half-lives prior to study entry (Screening) and/or during study participation;
4. Subjects with known prior participation (ie, randomized and received at least 1 dose of investigational product) in a study involving PF-05221304;
5. At Screening, subjects with a positive result for human immunodeficiency virus (HIV) antibodies, as assessed by sponsor-identified central laboratory, with a single repeat permitted to assess eligibility, if needed;
6. Male subjects with partners who are currently pregnant, pregnant female subjects, breastfeeding female subjects, as well as fertile male subjects and female subjects of childbearing potential who are unwilling or unable to use highly effective methods of contraception as outlined in [Section 4.4.4](#) for the duration of the study and for **at least 28 days** after the dose of investigational product;
7. Blood donation (excluding plasma donations) of approximately 1 pint (500 mL) or more within **60 days** prior to the dose of investigational product and until the on-site Follow-up visit (Day 7);
8. History of sensitivity to heparin or heparin-induced thrombocytopenia, **only if** heparin is used to flush intravenous catheters used during serial blood collections);
9. Unwilling or unable to comply with the Lifestyle Requirements outlined in [Section 4.4](#);
10. Subjects who are investigator site staff members directly involved in the conduct of the study and their family members, site staff members otherwise supervised by the investigator, or subjects who are Pfizer employees, including their family members, directly involved in the conduct of the study.

4.2.1. ***Additional*** Exclusion Criteria for Subjects without Hepatic Impairment (Cohort 1, ***only***)

In addition, subjects without hepatic impairment (Cohort 1) presenting with any of the following will ***not*** be included in the study:

1. Evidence of chronic liver disease including history of hepatitis, hepatitis B, or hepatitis C ***or*** evidence of ***any*** of the following, as assessed by sponsor-identified central laboratory, with a single repeat, permitted to assess eligibility, if needed –
 - Hepatitis B virus, defined by presence of hepatitis B surface antigen (HBsAg);
 - ***NOTE***: while ***not*** part of the tests assessed in this study, subjects with a previously positive HBsAb result due to vaccination, are deemed eligible;
 - Hepatitis C virus (HCV), defined by presence of hepatitis C antibody (HCVAb) and HCV RNA (when reflexed based on a positive result for HCVAb);
2. History of regular alcohol consumption exceeding 14 drinks/week for female subjects or 21 drinks/week for male subjects (1 drink = 5 ounces [150 mL] of wine or 12 ounces [360 mL] of beer or 1.5 ounces [45 mL] of hard liquor) within 6 months of before Screening;
3. Evidence or history of clinically significant hematological, renal, endocrine, pulmonary, gastrointestinal, cardiovascular, hepatic, psychiatric, neurologic, or allergic disease (including drug allergies, but excluding untreated, asymptomatic, seasonal allergies at the time of dosing);
4. Screening ***supine*** 12-lead ECG demonstrating QTcF interval >450 msec ***or*** a QRS interval >120 msec. If QTcF exceeds 450 msec, ***or*** QRS exceeds 120 msec, the ECG should be repeated 2 more times and the average of the ***three*** QTcF or QRS values should be used to determine the subject's eligibility;
5. Screening ***seated*** systolic blood pressure (SBP) ≥140 mm Hg ***or*** diastolic blood pressure (DBP) ≥90 mm Hg, following ≥5 minutes of seated rest. If SBP is ≥140 mm Hg ***or*** DBP ≥90 mm Hg, the BP assessment should be repeated 2 more times and the average of the ***three*** BP values should be used to determine the subject's eligibility;
6. Use of ***chronic*** prescription medications within **7 days or 5 half-lives** (whichever is longer) prior to Day 1 –
 - ***NOTE***: use of selected, limited prescription and non-prescription medications is permitted – refer to [Section 5.8.1](#) for details;

7. Other acute or chronic medical or psychiatric condition including recent (within the past year) or active suicidal ideation or behavior or laboratory abnormality that may increase the risk associated with study participation or investigational product administration or may interfere with the interpretation of study results and, in the judgment of the investigator, would make the subject inappropriate for entry into this study.

4.2.2. ***Additional*** Exclusion Criteria for Subjects with Impaired Hepatic Function (Cohorts 2, 3, and 4, ***only***)

In addition, subjects in the hepatic impairment cohorts (Cohorts 2, 3 and 4) presenting with ***any*** of the following will ***not*** be included in the study:

1. Hepatic carcinoma ***or*** hepatorenal syndrome ***or*** limited *predicted* life expectancy (defined as less than 1 year in Cohorts 2 & 3 and less than 6-months for Cohort 4 ***only***);
2. History of surgery that would be expected to alter Absorption, Distribution, Metabolism and Excretion (ADME) properties of PF-05221304 – ***for example***: status post porta-caval shunt surgery;
 - ***NOTE***: Subjects with a transjugular intrahepatic portosystemic shunt (TIPS) are permitted provided that they meet the Child-Pugh criteria;
3. History of gastrointestinal hemorrhage due to esophageal varices or peptic ulcers less than **4 weeks** prior to Screening;
4. At Screening, subjects with an estimated glomerular filtration rate (eGFR) of ≤ 60 mL/min using the Modification of Diet in Renal Disease (MDRD) equation, and serum creatinine (SCr), as assessed by the sponsor-identified central laboratory, with a single repeat permitted to assess eligibility, if needed;
5. Signs of clinically active Grade 3 or 4 hepatic encephalopathy (ie, $>$ Grade 2 Portal Systemic Encephalopathy score) – refer to [Appendix 2](#);
6. Severe ascites and/or pleural effusion, ***except*** for those categorized in Cohort 4 who may be enrolled provided subject is medically stable, per Investigators' medical judgment;
7. Subjects who have previously had a transplanted kidney, liver, or heart;
8. Screening ***supine*** 12-lead ECG demonstrating a QTcF interval >470 msec ***or*** a QRS interval >120 msec. If QTcF exceeds 470 msec, ***or*** QRS exceeds 120 msec, the ECG should be repeated 2 more times and the average of the 3 QTcF or QRS values should be used to determine the subject's eligibility;

9. At Screening, persistent severe, uncontrolled hypertension; for example: *seated* systolic blood pressure (SBP) ≥ 180 mm Hg and/or diastolic blood pressure (DBP) ≥ 105 mm Hg after ≥ 5 -minute of seated rest, with a single repeat permitted to assess eligibility, if needed, at each of these 2 visits:
 - For subjects with SBP ≥ 160 mm Hg **or** DBP ≥ 100 mm Hg, the period between Screening and Day -1 must be used to refine the doses of the agents used for management of blood pressure (refer to [Section 5.8.2](#)) with the aim to have stable BP on Day 1 [refer to [Section 4.3](#)];
10. Subjects with ALT **or** AST $>5x$ ULN on clinical laboratory tests at Screening, as assessed by the sponsor-identified central laboratory, with a single repeat permitted to assess eligibility, if needed.

4.3. Criteria for Dosing on Day 1

Subjects will progress to dosing on Day 1 provided they have satisfied **all** the following criteria –

- Eligibility criteria outlined in [Section 4.1](#) and [Section 4.2](#);
- Breath Alcohol test on Day -1 is negative;
- In females of childbearing potential, *urine* pregnancy test on Day 1 prior to dosing as reported by *on-site* pregnancy test using supplies offered by sponsor-identified central laboratory, is negative for pregnancy – refer to [Section 7.2.1.1](#);
- Safety-related laboratory tests collected and analyzed by sites' *local* laboratory on Day -1, *if performed* at investigator discretion, upon review on Day 1 must reflect subject to be in stable medical condition;
- **Cohorts 2, and 3, only:** patients with elevated BP at Screening must have measurement on Day 1 of SBP ≤ 159 mm Hg **and** DBP ≤ 99 mm Hg with repeat permitted, if needed, to confirm stable BP;
- **Cohort 4, only:** patients with elevated BP at Screening must have measurement on Day 1 of SBP ≤ 159 mm Hg **and** DBP ≤ 105 mm Hg with repeat permitted, if needed, to confirm stable BP.

